5.2 Description of efficacy variables

5.2.1 American College of Rheumatology (ACR) response

A participant is defined as an ACR20 responder if, and only if, the following three conditions hold:

[figure not shown]
- they have a $\geq 20\%$ improvement in the number of tender joints (based on 78 joints)
- they have a $\geq 20\%$ improvement in the number of swollen joints (based on 76 joints)
- they have a $\geq 20\%$ improvement in three of the following five domains:
 - Patient's global assessment of disease activity (PaGA) (measured on a VAS scale, 0-100)
 - Physician's global assessment of disease activity (PhGA) (measured on a VAS scale, 0-100)
 - Patient's assessment of PsA pain (measured on a VAS scale, 0-100)
 - Health Assessment Questionnaire – Disability Index (HAQ-DI©) score
 - Acute phase reactant (hsCRP or ESR)

ACR50 = 50% improvement in at least 3 of the 5 measures and 50% improvement in the swollen and tender joint count.

5.2.1.1 Tender 78 joint count and swollen 76 joint count

The 78 joints assessed for tenderness include the 2 temporomandibular, 2 sternoclavicular, 2 acromioclavicular joints, 2 shoulders, 2 elbows, 2 wrists, 2 first carpometacarpal, 10 metacarpophalangeal, 10 proximal interphalangeal, 8 distal interphalangeal joints of the hands, the 2 hip, 2 knee, 2 talo-tibial, 2 mid-tarsal, 10 metatarsophalangeal, 10 proximal interphalangeal, and 8 distal interphalangeal joints of the feet. All of these except for the hips are assessed for swelling. Joint tenderness and swelling are to be graded present (1) or absent (0). Synovial fluid and/or soft tissue swelling but not bony overgrowth represents a positive result for swollen joint count.

[REDACTED]. These aspects are to be implemented during data capture and will not be addressed during programming.

If the number of joints for which data were available (e.g., T) is less than 78/76 for the tender/swollen joint assessment, the number of tender/swollen joints (e.g., t) will be scaled up proportionately (i.e., $78*t/T$ or $76*t/T$ for tender or swollen joint count).

Data is recorded for tender and swollen joints (right or left side), i.e., a box (yes, no or not applicable) needs to be ticked for all joints.

5.2.1.2 Patients' global assessment of disease activity

The patient's global assessment of disease activity will be performed using a Visual Analog Scale (VAS) of 100 mm ranging from "0 -very good" to "100= very poor", after the question '*Considering all the ways Psoriatic Arthritis affects you, please indicate with a vertical mark (|) through the horizontal line how well you are today*'.

5.2.1.3 Physicians' global assessment of disease activity

The PhGA will be performed using 100 mm VAS ranging from no disease activity to maximal disease activity, after the question '*Considering all the ways the disease affects your patient, draw a line on the scale for how well his or her condition is today*'. To enhance objectivity, the physician must not be aware of the specific patient's global assessment of disease activity, when performing his own assessment on that participant.

5.2.1.4 Patients' assessment of PsA pain

The patient's assessment of pain will be performed using 100 mm visual analog scale (VAS) ranging from 'no pain' to 'unbearable pain' after the question '*Please indicate with a vertical mark (|) through the horizontal line the most pain you had from your psoriatic arthritis today*'.

5.2.1.5 Health Assessment Questionnaire Disability Index (HAQ- DI[©])

The Health Assessment Questionnaire (HAQ[©]) was developed by Stanford University and is one of the most widely used measures to assess the long-term influence of chronic disease on a subject's level of functional ability and activity restriction. The disability assessment component of the HAQ (Health Assessment Questionnaire – Disability Index), the HAQ-DI[©], assesses a subject's level of functional ability and includes questions of fine movements of the upper extremity, locomotor activities of the lower extremity, and activities that involve both upper and lower extremities. There are 20 questions in eight categories of functioning including dressing, rising, eating, walking, hygiene, reach, grip, and usual activities. The stem of each item asks over the past week "Are you able to ..." perform a particular task. Each item is scored on a 4-point scale from 0 to 3, representing normal (normal, no difficulty [0]), some difficulty [1], much difficulty [2], and unable to do [3].

Scoring of the HAQ-DI[©]

The HAQ-DI[©] will be scored in accordance with the Alternative Disability Index (ADI) scoring as described in Wolfe F (2001), Zandbelt et al (2001) and the HAQ instruction [10]. The use of ADI scoring is due to how the data was collected for the "use of aids, devices, or help from

another person" questions. The ADI scoring does not include data collected from "use of aids, devices, or help from another person" questions in the calculation of scores. The ADI is one of the two disability indices described in HAQ instruction, to reflect the disability level of a subject when using aids and devices to compensate for disability. The HAQ-DI[®] using ADI scoring method was efficient and sensitive to change, and performed well to detect mild functional loss (Wolfe F, 2001).

The following coding is to be used for the 20 items of the 8 categories of the disability outcome dimension:

Without ANY Difficulty	0
With SOME Difficulty	1
With MUCH Difficulty	2
UNABLE to do	3

The score for each category will be the single response of the item with the highest score (greatest difficulty) within that category. For example, in the "Arising" category, there are two items: 1. "Are you able to stand up from a straight chair"; 2. "Are you able to get in and out of bed". If "Are you able to stand up from a straight chair" is marked as "3" and "Are you able to get in and out of bed" is marked as "0", then the score for the "Arising" category would be "3".

Therefore, the highest score reported by the subject for any component question of the eight categories determines the score for that category. If a component question is left blank, then the score of that category will be determined by the remaining completed question(s).

An ADI is computed by summing the computed scores for each category and then divided by the number of categories answered. The ADI is not computed if the subject does not have scores for at least 6 categories. The ADI is the HAQ-DI[®] score, which will be used in the statistical analyses of this instrument, e.g., ACRn calculation, HAQ-DI[®] change from baseline. The range for HAQ-DI[®] score is (0, 3).

HAQ-DI[®] response is defined by an improvement of at least 0.35 score points compared to baseline.

5.2.1.6 High Sensitivity C-reactive protein (hsCRP)

Blood for this assessment will be obtained in order to identify the presence of inflammation, to determine its severity, and to monitor response to treatment.

Since the results of this test may unblind study personnel, results from the central lab will be provided for screening and BSL only. The hsCRP results from samples collected during the treatment period will be revealed following database lock only.

5.2.1.7 Erythrocyte sedimentation rate (ESR)

Blood for ESR, which is helpful in diagnosing inflammatory disease and is used to monitor disease activity and response to therapy, will be obtained at scheduled visits.

Local ESR test will be performed.

5.2.2 DAS28 and EULAR response

DAS28, low disease activity and remission

The Disease Activity Score (DAS) is a combined index to measure the disease activity in patients with RA. It has been extensively validated for its use in clinical trials in combination with the EULAR response criteria.

The DAS28 is a measure of disease activity based on Swollen and Tender Joint Counts, CRP or ESR, and the Patient Global Assessment of PsA disease activity.

The following 28 joints will be assessed for tenderness and swelling: metacarpophalangeal IV (10), thumb interphalangeal (2), hand proximal interphalangeal II-V (8), wrist (2), elbow (2), shoulders (2), and knees (2).

The following formulas can be used to calculate the DAS28 with CRP (mg/L) or ESR (mm/hour).

$$\text{DAS28-CRP} = 0.56 * \text{sqrt}(\text{TJC28}) + 0.28 * \text{sqrt}(\text{SJC28}) + 0.36 * \ln(\text{CRP}+1) + 0.014 * \text{PGA} + 0.96$$

$$\text{DAS28-ESR} = 0.56 * \text{sqrt}(\text{TJC28}) + 0.28 * \text{sqrt}(\text{SJC28}) + 0.70 * \ln(\text{ESR}) + 0.014 * \text{PGA}$$

TJC28: 28 Tender joint count; SJC28: 28 Swollen joint count; CRP: C-reactive protein; PGA: Patient Global Assessment

If any component measurement is missing, DAS28 will be missing.

DAS28-CRP will be primarily used for the interpretation of the outcome; DAS-ESR is considered supportive.

DAS28-CRP (or ESR) remission is defined as a DAS28-CRP (or ESR) index score less than 2.6. Low disease activity is defined as DAS28-CRP (or ESR) index less than or equal to 3.2.

EULAR response

Using the DAS, several thresholds have been developed for high disease activity, low disease activity or remission. Also, response criteria have been developed based on the DAS, so when the DAS of a patient is measured at two time-points (e.g., before the start of a treatment and after 3 months), the patient's clinical response can be assessed.

Comparing the DAS28-CRP (or ESR) from one patient on two different time-points, it is possible to define improvement or response. The EULAR response criteria are defined as follows:

Table 5-3 EULAR response criteria

Present DAS28	DAS28 improvement		
	>1.2	0.6-1.2	<0.6
<3.2	Good response	Moderate response	No response

3.2-5.1	Moderate response	Moderate response	No response
>5.1	Moderate response	No response	No response

Both the thresholds for high and low disease activity and remission and the above mentioned improvement criteria are used to interpret the DAS28 scores.

5.2.3 Psoriatic Arthritis Disease Activity Score (PASDAS)

PASDAS is a new composite measure developed to access disease activity in Psoriasis (GRACE Project) (Helliwell et al 2012). It is calculated by utilizing seven measures; the seven components are: Patient reported measures [REDACTED]

[REDACTED] skin, peripheral joint counts (Tender and Swollen joint counts), [REDACTED] acute phase response (CRP) and Patient & Physician global VAS scores.

$$\begin{aligned} \text{PASDAS} = & (0.18 \times \sqrt{\text{Physician global VAS}}) \\ & + (0.159 \times \sqrt{\text{Patient global VAS}}) \\ & - (0.253 \times \sqrt{\text{SF36-PCS}}) \\ & + (0.101 \times \text{LN}(\text{Swollen joint count} + 1)) \\ & + (0.048 \times \text{LN}(\text{Tender joint count} + 1)) \\ & [REDACTED] \\ & [REDACTED] \\ & + (0.102 \times \text{LN}(\text{CRP} + 1)) + 2) * 1.5 \end{aligned}$$

If any component measurement is missing, PASDAS will be missing. The patient global VAS defined in the PASDAS score is “VAS for PASDAS assessment” which measures patient’s global assessment of PSORIASIS and ARTHRITIS disease activity. The Physician global VAS is the Physician’s global assessment of PsA disease activity. Tender Dactylitis count is from “Leeds Dactylitis Instrument” CRF page with “Was dactylitis present?” = “Yes” and “Tender/non-tender” = “Tender”.

[figure not shown]
[figure not shown]
66-swollen / 68-tender joint counts for PASDAS assessment:

[figure not shown]
There are only 66 swollen and 68 tender joint counts which will be used for PASDAS assessment. That is the 10 joints in CRF: CMC1, DIP2 (FOOT), DIP3 (FOOT), DIP4 (FOOT), and (DIP5 (FOOT) both left and right, should not be counted in the swollen/tender joint count in PASDAS formula.

[figure not shown]
[figure not shown]
If the number of joints for which data were available (e.g., T) is less than 66/68 for the swollen/tender joint assessment, the number of swollen/tender joints (e.g., t) will be scaled up proportionately (i.e., $66*t/T$ or $68*t/T$ for swollen or tender joint count).

5.2.3.1 VAS for PASDAS assessment

Global Disease Activity: The patient's assessment of psoriasis and arthritis will be performed using 100 mm VAS ranging from 'Excellent' to 'Poor' after the question '*Considering all the ways PSORIASIS and ARTHRITIS affects you, please indicate with a vertical mark (|) through the horizontal line how well you are doing over the past week*'.

5.3 Imputation rules

5.3.1 Study drug

Any partial dates will be imputed as follows:

We take the earlier day of

- The last day in the month and
- The end day of the corresponding epoch

5.3.2 AE date imputation

Impute AE end date:

1. If the AE end date ‘month’ is missing, the imputed end date should be set to the earliest of the (min (last visit date, last dose data + 84 days), 31DECYYYY, date of death).
2. If the AE end date ‘day’ is missing, the imputed end date should be set to the earliest of the (min (last visit date, last dose data + 84 days), last day of the month, date of death)
3. If AE ‘year’ is missing or AE is ongoing, the end date will not be imputed.

Impute AE start date:

Before imputing AE start date, find the AE start reference date.

1. If the (imputed) AE end date is complete and the (imputed) AE end date < treatment start date then AE start reference date = min(informed consent date, earliest visit date).
2. Else AE start reference date = treatment start date
 1. If the AE start date ‘year’ value is missing, the date uncertainty is too high to impute a rational date. Therefore, if the AE year value is missing, the imputed AE start date is set to NULL.
 2. If the AE start date ‘year’ value is less than the treatment starts date year value, the AE started before treatment. Therefore:
 - a. If AE ‘month’ is missing, the imputed AE start date is set to the mid-year point (01JulYYYY).
 - b. Else if AE ‘month’ is not missing, the imputed AE start date is set to the mid-month point (15MONYYYY).
 3. If the AE start date year value is greater than the treatment starts date year value, the AE started after treatment. Therefore:
 - a. If the AE month is missing, the imputed AE start date is set to the year start point (01JanYYYY).
 - b. Else if the AE month is not missing, the imputed AE start date is set to the later of (month start point (01MONYYYY), AE start reference date + 1 day).
4. If the AE start date year value is equal to the treatment start date year value:
 - a. And the AE month are missing the imputed AE start date is set to the AE reference start date + 1 day.
 - b. Else if the AE month is less than the treatment start month, the imputed AE start date is set to the mid-month point (15MONYYYY).

- c. Else if the AE month is equal to the treatment start date month or greater than the treatment starts date month, the imputed AE start date is set to the later of (month start point (01MONYYYY), AE start reference date + 1 day).

If complete (imputed) AE end date is available and the imputed AE start date is greater than the (imputed) AE end date, then imputed AE start date should be set to the (imputed) AE end date.

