The appropriate personnel from the site and Novartis will assess whether study treatment should be discontinued for any participant whose treatment code has been broken inadvertently for any reason.

Participants who prematurely discontinued from study treatment during Treatment Period 1 had to return for assessments associated with End of TP1 visit (4 weeks after the last study treatment) and the End of study visit (12 weeks after the last study treatment). Participants who prematurely discontinued during Treatment Period 2 had to return and complete assessments associated with End of TP2 visit (4 weeks after the last study treatment) and End of study visit (12 weeks after the last study treatment) and End of study visit (12 weeks after the last study treatment) and End of study visit (12 weeks after the last study treatment) and End of study visit (12 weeks after the last study treatment) and End of study visit (12 weeks after the last study treatment) and End of study visit (12 weeks after the last study treatment) and End of study visit (12 weeks after the last study treatment) and End of study visit (12 weeks after the last study treatment) and End of study visit (12 weeks after the last study treatment) and End of study visit (12 weeks after the last study treatment) and End of study visit (12 weeks after the last study treatment) and End of study visit (12 weeks after the last study treatment) and End of study visit (12 weeks after the last study treatment).

- Participants unwilling to continue attending further study visits after prematurely discontinuing the study treatment should return for the end of study (EOS) visit 12 weeks after the last administration of the study treatment.
- Participants willing to continue attending study visit should continue attending all subsequent scheduled site visits for clinical and safety study assessments, except study treatment administration.
- Participants initially continue attending site visits after premature study treatment discontinuation may decide to discontinue study at any time. For those participants, the EOS visit will be performed at time of study discontinuation. Note: the EOS visit must always be completed at least 12 weeks after the last study treatment administration.

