2.7.1 Adverse events (AEs)

Treatment-emergent adverse events (i.e., events started after the first dose of study treatment or events present prior to the first dose of study treatment but increased in severity based on preferred term and on or before last dose + 84 days) will be summarized.

Adverse events will be summarized by presenting, for each treatment group, the number and percentage of participants having any AE, having an AE in each primary system organ class and having each individual AE (preferred term). Summaries will also be presented for AEs by severity and for study treatment related AEs. If a participant reported more than one adverse event with the same preferred term, the adverse event with the greatest severity will be presented. If a participant reported more than one adverse event within the same primary system organ class, the participant will be counted only once with the greatest severity at the system organ class level, where applicable. Serious adverse events will also be summarized.

These summaries may be presented separately by placebo controlled period and entire study.

As appropriate, the incidence of AEs will be presented per 100 patient years of exposure (exposure-adjusted incidence rates).

Separate summaries will be provided for death, serious adverse event, other significant adverse events leading to discontinuation and adverse events leading to dose adjustment (including study treatment discontinuation).

A graphical display of relative frequencies within system organ classes and relative risks, as appropriate, will be presented.

Adverse events will also be reported separately by Standardized MedDRA Query (SMQ) according to MedDRA. The MedDRA version used for reporting the study will be described in a footnote.

Treatment emergent and non-treatment emergent adverse events will be listed.

Algorithms for date imputations will be provided in Programming Datasets Specifications.

For serious adverse events (SAEs) occurred during screening a listing were prepared for all subjects screened including screening failures at the primary endpoint analysis.

The safety analysis that will be performed for treatment emergent AEs and on treatment labs and vital signs for each analysis period is described in Table 2-1.

The data in the period of Day 1 – Week 16 were presented at the primary endpoint analysis; the data in the period of Entire treatment will be presented at the Final Analysis.

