5.3.3 Concomitant medication date imputation

Impute CM end date:

1. If CM end day is missing and CM month/year are non-missing, then impute CM day as the minimum of treatment end date and the last day of the month.
2. If CM end day/month are missing and CM year is non-missing, then impute CM day as the minimum of treatment end date and the end of the year (31DECYYYY).
3. If imputed CM end date is less than the CM start date, use the CM start date as the imputed CM end date.

Impute CM start date:

1. If the CM start date year value is missing, the imputed CM start date is set to one day prior to treatment start date.
2. If the CM start date year value is less than the treatment starts date year value, the CM started before treatment. Therefore:
 - a. If the CM month is missing, the imputed CM start date is set to the mid-year point (01JULYYYY)
 - b. Else if the CM month is not missing, the imputed CM start date is set to the mid-month point (15MONYYYY)
3. If the CM start date year value is greater than the treatment starts date year value, the CM started after treatment. Therefore:
 - a. If the CM month is missing, the imputed CM start date is set to the year start point (01JANYYYY)
 - b. Else if the CM month is not missing, the imputed CM date is set to the month start point (01MONYYYY)
4. If the CM start date year value is equal to the treatment start date year value:
 - a. And the CM month is missing, or the CM month is equal to the treatment start date month, then the imputed CM start date is set to one day prior treatment start date
 - b. Else if the CM month is less than the treatment starts date month, the imputed CM start date is set to the mid-month point (15MONYYYY)
 - c. Else if the CM month is greater than the treatment starts date month, the imputed CM start date is set to the month start point (01MONYYYY)

If complete (imputed) CM end date is available and the imputed CM start date is greater than the (imputed) CM end date, then imputed CM start date should be set to the (imputed) CM end date.

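### The rule for partial AE end dates has no floor, so an event after last dose + 84 days can be moved back into the treatment-emergent window or given an end before its start

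*SAP*

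**What the plan says.** SAP 5.3.2 fills in partial AE dates.

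- End date without a day: "the imputed end date should be set to the earliest of the (min (last visit date, last dose data + 84 days), last day", meaning that of the recorded month, and death.
- End date without a month: "the imputed end date should be set to the earliest of the (min (last visit date, last dose data + 84 days), 31DECYYYY, date of death".
- Exempt: if the year is missing or the "AE is ongoing, the end date will not be imputed".
- Start date, month known and not before the month of first dose: "the imputed AE start date is set to the later of (month start point (01MONYYYY), AE start reference date + 1 day".
- Conflict: if the imputed start is later than the end, "then imputed AE start date should be set to the (imputed) AE end date".

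SAP 2.7.1 counts an AE as treatment-emergent when it starts, or worsens, after first dose and "on or before last dose + 84 days". SAP 2.1.1.2 defines duration as end minus start plus one. SAP 2.4.1 ends exposure time at the earlier of last dose + 84 days and last visit.

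For concomitant medication, SAP 5.3.3 has a repair that the AE section lacks: "If imputed CM end date is less than the CM start date, use the CM start date as the imputed CM end date".

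On follow-up after stopping treatment, Protocol 9.1.1 says: "Participants willing to continue attending study visit should continue attending all subsequent scheduled site visits for clinical and safety study assessments". The same section makes AEs part of the minimum data after discontinuation. Protocol 10.1.1 sets 12 weeks after last dose as a minimum for AE monitoring, not as its end.

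**The concern.** The start-date rule respects the recorded month, but the end-date rule does not. If the recorded end month lies after the cap, the cap wins and the imputed end falls before the month the site wrote down. The closing sentence of 5.3.2 then overrides the start-date rule as well and moves an imputed start to the same day.

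That day is at or before last dose + 84 days, so it meets the inclusive limit in SAP 2.7.1. An event whose recorded month lies outside the window would then enter the TEAE tables and the numerator of the exposure-adjusted rates, while the person-time stops at the cap.

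The closing sentence covers imputed starts only. A complete start is left alone, so the event ends before it begins.

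**Working it through.** The plan states no figure to reproduce. The check applies the rule as written to illustrative dates.

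**Inputs**
- Cap C = min(last visit, last dose + 84 days). Imputed end E = min(C, end of recorded month or year, death). SAP 5.3.2.
- Imputed start S = max(first of recorded month, start reference date + 1 day); if S > E, then S = E. SAP 5.3.2.
- Treatment-emergent if the onset is after first dose and on or before last dose + 84 days. SAP 2.7.1.
- Duration = E − S + 1. SAP 2.1.1.2.
- Target days: Week 4 = 29, Week 12 = 85, Week 36 = 253, Week 48 = 337, Week 52 = 365 (SAP Table 5-1). F60 is eight weeks after Week 52: 365 + 56 = Day 421.

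**Example 1: stops after Week 4, keeps attending.** First dose 10 Jan 2022; last dose Day 29 = 7 Feb 2022; C = 7 Feb + 84 = 2 May 2022 (Day 113).
- Start SEP2022, end SEP2022: E = min(2 May, 30 Sep) = 2 May. S = max(1 Sep, 11 Jan) = 1 Sep, later than E, so S = 2 May. The event is treatment-emergent, dated 122 days before 1 Sep.
- Start 12 Sep 2022, end SEP2022: E = 2 May. Duration = 2 May − 12 Sep + 1 = −133 + 1 = −132 days. Not treatment-emergent.

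**Example 2: stops after Week 12, keeps attending.** First dose 1 Mar 2021; last dose 24 May 2021; C = 16 Aug 2021; last visit 25 Apr 2022.
- Start NOV2021, end DEC2021: both become 16 Aug 2021, treatment-emergent, duration 1 day.
- Start 10 Nov 2021, end DEC2021: E = 16 Aug; duration −86 + 1 = −85 days.
- Start 10 Jan 2022, end year 2022 only: E = 16 Aug 2021; duration −146 days.
- Start 20 Aug 2021, end AUG2021: E = 16 Aug; duration −3 days, although the recorded month contains the cap.

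Over 1,151 combinations of post-window onset and duration (0, 5, 14, 30 or 60 days) on these dates, with the end day missing, every partial start landed inside the window and every complete start fell after its imputed end. Partial starts in the cap's own month are included in that count; they are imputed to the first of that month and are usually treatment-emergent whatever the end rule does.

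**Controls on the Example 2 dates**
- Start NOV2021 with a complete end (5 Dec 2021) or ongoing: S stays at 1 Nov, outside the window.
- Start 1 Aug 2021, end DEC2021: still treatment-emergent, correctly; only the duration changes, 16 days instead of up to 153.

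**Who can be affected.** Days between cap and F60 = 421 − (last dose day + 84).
- Last dose Week 12: 421 − 169 = 252.
- Last dose Week 36: 421 − 337 = 84.
- Last dose Week 48: 421 − 421 = 0.

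A completer is exposed only if F60 is late. With F60 on Day 428, an AE starting on Day 423 with only the end month known is given an end on Day 421: duration 421 − 423 + 1 = −1.

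**The case against.** The strongest reply is that the conditions rarely coincide. A false treatment-emergent count needs an early stop or a late final visit, follow-up beyond last dose + 84 days, onset after that date, a partial end that is not ongoing, and a partial start. Continued attendance applies only to willing participants; the others have a final visit 12 weeks after last dose. After 12 weeks, Protocol 10.1.3 asks for SAEs only if causally suspected. Safety is descriptive, and SAP 2.7.1 lists both treatment-emergent and other AEs, so nothing is hidden. All of this stands and limits the size.

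SAP 2.7.1 also leaves date-imputation algorithms to the Programming Datasets Specifications, which are not available here. A guard may exist there, but 5.3.2 states its own rule in full without one.

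Stronger readings that a reader might infer are not supported:

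- That every partial end date is distorted. Year-missing and ongoing events are exempt, and a recorded month that ends before the cap is handled properly.
- That negative durations corrupt TEAE or occurrence counts. Those events have complete starts after the window, so they are not treatment-emergent and do not reach those tables. SAP 2.7 plans no AE-duration table.
- That one event should be sized against a treatment-sequence column. Someone who stops in Treatment Period 1 is not re-randomized (Protocol 6.3.2) and has no two-period sequence.
- That the 84-day cap should be removed because the treatment-emergent definition already applies it. That definition governs onset or worsening, not end dates.

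**Conclusion.** The point holds as a drafting error of limited reach. For an AE with onset after last dose + 84 days and an end date lacking day or month, the written rule gives one of two wrong results:

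- Start also partial, in a later month than the cap: the event is dated to the cap and counted as treatment-emergent, against its recorded month.
- Start complete: the end precedes the start. This is a listing defect.

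The displacement is deterministic for each event and can run to months. The number of such events cannot be derived from the documents and is probably small. On-schedule completers are essentially unaffected, and neither the primary result nor any other efficacy result is touched.

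This assumes that 5.3.2 is programmed as written, that the 84-day limit in SAP 2.7.1 applies to new events as well as worsened ones, and that the last visit is not before last dose + 84 days; if it is, the cap is earlier still. If programmers applied the closing rule to complete starts too, those events would also move into the window.

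**What to change.** Keep the cap and add two sentences to SAP 5.3.2:

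1. An imputed AE end date may not be earlier than the AE start date or the first day of its recorded month (or year, if the month is missing).
2. An imputed AE start date may not be moved before the first day of its recorded month (or year).

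The start-date floor in sentence 1 mirrors item 3 of SAP 5.3.3. Apply the recorded-period floors first, then raise the end to the start if it is still earlier.

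Results under the amended rule:
- SEP2022/SEP2022 (Example 1): start and end 1 Sep 2022, outside the window.
- Start 12 Sep 2022, end SEP2022: end 12 Sep, duration 1 day.
- Start 20 Aug 2021, end AUG2021: end 20 Aug, duration 1 day. The recorded-month floor alone would leave −3, so the start-date floor is needed.
- Start SEP2022, end year 2022 only (Example 1): the end's year floor, 1 Jan 2022, does not bind, but sentence 2 holds the start at 1 Sep and the end is raised to match.

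Cost: two sentences, a small change to the AE derivation and a matching check of the programming specifications before the final database lock. No new data are needed, and the treatment-emergent definition is unchanged.
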